5.3 Baseline Procedures

During this period, we will get baseline assessments of parameters of interest.

5.3.1 Baseline Visit 1

- Return 24-hour urine collection to measure phosphorus, creatinine, calcium, and urea in the urine
- Random urine sample to measure phosphorus, creatinine, and calcium in the urine
- 8-hour CRU stay for 8-hour timed urine collection to measure phosphorus, creatinine, calcium and urea in the urine
- Plasma chemistries (creatinine, phosphate, calcium)
- Blood draw for correlative studies (PTH, FGF23, P1NP, CTX)
- Blood draw for optional study elements (PTH, FGF23, P1NP, CTX)
- Distribute supplies for 24-hr urine collection

5.4 Procedures During Treatment

During this period, participants will be randomized to the intervention arms (Baseline 2/ Follow up visit 0), have two 8-hour visits (Baseline visits 1 and Follow up visit 5) and will make visits to the CTMH every 3 days (Follow up visits 1 – 4).

5.4.1 Baseline 2/Follow-up Visit 0 (F0)

- Return 24-hour urine collection to measure phosphorus, creatinine, calcium, and urea in the urine
- Random urine sample to measure phosphorus, creatinine, and calcium in the urine
- Plasma chemistries (NA, K, Cl, HCO3, BUN, Cr, glucose, phosphate, calcium)
- Blood draw for correlative studies (PTH, FGF23)
- Randomization to interventions
- Distribute study drug/placebo
- Distribute supplies for next 24-hr urine collection

5.4.2 Follow-up Visits 1 – 4 (F1-F4)

- Return 24-hour urine collection to measure phosphorus, creatinine, calcium, and urea in the urine
- Plasma chemistries(NA, K, Cl, HCO3, BUN, Cr, glucose, calcium)
- Blood draw for correlative studies (PTH, FGF23)
- Random urine sample to measure phosphorus, creatinine, and calcium in the urine
- Distribute supplies for next 24-hr urine collection
- Bring in pill bottles for pill counts
- Safety assessments (phosphate, CK, CBC, LFTs, GI Questionnaire)

5.4.3 Follow-up Visit 5 (F5)

- Return 24-hour urine collection to measure phosphorus, creatinine, calcium, and urea in the urine
- Random urine sample to measure phosphorus, creatinine, and calcium in the urine
- 8-hour CRU stay for 8-hour timed urine collection to measure phosphorus, creatinine, calcium and urea in the urine

- Plasma chemistries (NA, K, Cl, HCO3, BUN, Cr, glucose, calcium)
- Safety assessments (phosphate, CK, CBC, LFTs, GI Questionnaire)
- Blood draw for correlative studies (PTH, FGF23, P1NP, CTX)
- Blood draw for optional study elements (PTH, FGF23, P1NP, CTX)
- Bring in pill bottles for pill counts

5.5 Time and Events Table

Periods	SCREENING	BASELINE		Follow UP				
		F1	F2	F3	F4	F5		
Visits	S1	B1	B2/F0					
Days	-15	-5	-2	0	3	6	9	12
Pregnancy testing	X							
RANDOMIZATION				X				
Distribute drug/placebo (X=21 day supply)				X				
Demographics, medical history, physical exam	X							
Vital signs (blood pressure, height, weight)	X							
Co-Primary end-points								
FePI/ Spot Urine phosphate, calcium, and creatinine		X	X	X	X	X	X	X
24-hr urine phosphate, creatinine, calcium, and urea		X	X	X	X	X	X	X
8 hr urine phosphate, creatinine, calcium, and urea		X						X
Spot Urine (creatinine, albumin)	X							
Other mineral metabolites								
PTH		X	X	X	X	X	X	X
FGF23		X	X	X	X	X	X	X
P1NP (bone metabolism marker)		X						X
CTX (bone metabolism marker)		X						X
25 hydroxyvitamin D	X							
Plasma Phosphate	X	X	X	X	X	X	X	X
Plasma Calcium	X	X	X	X	X	X	X	X
Renal parameters								
Chem 7 (Na, K, Cl, HCO3, BUN, Cr, glucose)	X		X	X	X	X	X	X
Plasma Creatinine		X						
Stored blood samples (optional)		X						X
Stored urine samples (optional)		X						X
CBC, LFTs, CK	X			X	X	X	X	X
Adverse events assessment (labs and GI questionnaire)				X	X	X	X	X
Pill Count				X	X	X	X	X

5.6 Removal of Subjects from Study

Patients can be taken off the study treatment and/or study at any time at their own request, or they may be withdrawn at the discretion of the investigator for safety, behavioral or administrative reasons. The reason(s) for discontinuation will be documented.

6.0 Response Criteria

Plasma Phosphate levels, CBC, LFTs, CK will be monitored as safety labs through the intervention period.

6.1 Safety/tolerability

Analyses of safety will be performed for all patients having received at least one dose of study drug.

7.0 ADVERSE EVENTS**7.1 Adverse Event Monitoring**

Adverse event data collection and reporting, which are required as part of every clinical trial, are done to ensure the safety of subjects enrolled in the studies as well as those who will enroll in future studies using similar agents. Adverse events are reported in a routine manner at scheduled times during a trial. Additionally, certain adverse events must be reported in an expedited manner to allow for optimal monitoring of patient safety and care.

All patients experiencing an adverse event, regardless of its relationship to study drug/device, will be monitored until:

- the adverse event resolves or the symptoms or signs that constitute the adverse event return to baseline;
- any abnormal laboratory values have returned to baseline;
- there is a satisfactory explanation other than the study drug for the changes observed; or
- death.

7.2 Definitions**7.2.1 Definition of Adverse Event**

An adverse event (AE) is any untoward medical occurrence in a patient receiving study treatment and which does not necessarily have a causal relationship with this treatment. An AE can therefore be any unfavorable and unintended sign (including an abnormal laboratory finding), symptom, or disease temporally associated with the use of an experimental intervention, whether or not related to the intervention.

7.2.2 Severity of Adverse Events

The severity of an AE is graded as follows:

Mild (grade 1): the event causes discomfort without disruption of normal daily activities.

Moderate (grade 2): the event causes discomfort that affects normal daily activities.

Severe (grade 3): the event makes the patient unable to perform normal daily activities or significantly affects his/her clinical status.

Life-threatening (grade 4): the patient was at risk of death at the time of the event.

Fatal (grade 5): the event caused death.

7.2.3

Serious Adverse Events

A “serious” adverse event is defined in regulatory terminology as any untoward medical occurrence that:

7.2.3.1 Results in death.

If death results from (progression of) the disease, the disease should be reported as event (SAE) itself.

7.2.3.2 Is life-threatening.

(the patient was at risk of death at the time of the event; it does not refer to an event that hypothetically might have caused death if it were more severe).

7.2.3.3 Requires in-patient hospitalization or prolongation of existing hospitalization for ≥ 24 hours.

7.2.3.4 Results in persistent or significant disability or incapacity.

7.2.3.5 Is a congenital anomaly/birth defect

7.2.3.6 Is an important medical event

Any event that does not meet the above criteria, but that in the judgment of the investigator jeopardizes the patient, may be considered for reporting as a serious adverse event. The event may require medical or surgical intervention to prevent one of the outcomes listed in the definition of “Serious Adverse Event”. For example: allergic bronchospasm requiring intensive treatment in an emergency room or at home; convulsions that may not result in hospitalization; development of drug abuse or drug dependency.

7.3 Steps to Determine If an Adverse Event Requires Expedited Reporting

Step 1: Identify the type of adverse event

Step 2: Grade the adverse event

Step 3: Determine whether the adverse event is related to the protocol therapy
Attribution categories are as follows:

- Definite – The AE is *clearly related* to the study treatment.
- Probable – The AE is *likely related* to the study treatment.
- Possible – The AE *may be related* to the study treatment.
- Unrelated – The AE is *clearly NOT related* to the study treatment.

Note: This includes all events that occur within 30 days of the last dose of protocol treatment. Any event that occurs more than 30 days after the last dose of treatment and is attributed (possibly, probably, or definitely) to the agent(s) must also be reported accordingly.

Step 4: Determine the prior experience of the adverse event.

Expected events are those that have been previously identified as resulting from administration of the agent. An adverse event is considered unexpected, for expedited reporting purposes only, when either the type of event or the severity of the event is not listed in:

- the current known adverse events listed in the Agent Information Section of this protocol;
- the drug package insert;
- the current Investigator's Brochure

7.4 Reporting Requirements for Adverse Events

7.4.1

Expedited Reporting

- The Principal Investigator must be notified within 24 hours of learning of any serious adverse events, regardless of attribution, occurring during the study or within 30 days of the last administration of the study drug.
- The IRB must be notified within 10 business days of "any unanticipated problems involving risk to subjects or others" (UPR/UPIRSO).

The following events meet the definition of UPR:

1. Any serious event (injuries, side effects, deaths or other problems), which in the opinion of the Principal Investigator was unanticipated, involved risk to subjects or others, and was possibly related to the research procedures.
2. Any serious accidental or unintentional change to the IRB-approved protocol that alters the level of risk.
3. Any deviation from the protocol taken without prior IRB review to eliminate apparent immediate hazard to a research subject.
4. Any new information (e.g., publication, safety monitoring report, updated sponsor safety report), interim result or other finding that indicates an unexpected change to the risk/benefit ratio for the research.
5. Any breach in confidentiality that may involve risk to the subject or others.
6. Any complaint of a subject that indicates an unanticipated risk or that cannot be resolved by the Principal Investigator.

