10.1	Study Design/Study Endpoints	17
10.2	Sample Size and Accrual	18
10.3	Data Analyses Plans.....	19

11.0	STUDY MANAGEMENT	19
11.1	Conflict of Interest.....	19
11.2	Institutional Review Board (IRB) Approval and Consent.....	19
11.3	Registration Procedures	20
11.4	Subject Compensation.....	19
11.5	Data Management and Monitoring/Auditing	20
11.6	Adherence to the Protocol	20
11.7	Amendments to the Protocol	21
11.8	Record Retention.....	21
11.9	Obligations of Investigators	21
12.0	REFERENCES	23
13.0	APPENDICES.....	24

LIST OF ABBREVIATIONS

CKD	chronic kidney disease
CBC	complete blood counts
CVD	cardiovascular disease
ESRD	end-stage renal disease
FGF23	fibroblast growth factor 23 hormone
LVH	left ventricular hypertrophy
NPT2b	sodium phosphate co-transporter
PTH	parathyroid hormone
FEPi	Fractional excretion of phosphate
P1NP	N terminal propeptide of Type 1 procollagen, bone formation marker
CTX	C terminal cross-linked peptide, bone resorption marker
LC	Lanthanum Carbonate
N	Nicotinamide

STUDY SCHEMA

LC, Lanthanum carbonate

N, Nicotinamide

STUDY SUMMARY

Title	EFFECTS OF NICOTINAMIDE AND LANTHANUM CARBONATE ON PHOSPHORUS HOMEOSTASIS
Short Title	Nicotinamide, lanthanum carbonate and phosphate homeostasis
Protocol Number	The standard protocol number used to identify this study
Phase	Phase 1, detailed physiologic study
Methodology	double blind, randomized, placebo-controlled, 2x2 factorial
Study Duration	12-18 months (to complete the entire study protocol)
Study Center(s)	Single-center
Objectives	Define short-term effects of the interventions (lanthanum carbonate and nicotinamide) on indices of phosphate handling
Number of Subjects	80
Diagnosis and Main Inclusion Criteria	Healthy volunteers
Study Product(s), Dose, Route, Regimen	Nicotinamide, 750 mg by mouth twice daily Lanthanum carbonate, Fosrenol, 1000 mg by mouth three times daily with meals
Duration of administration	2 weeks (length of time study participants are enrolled in study)
Reference therapy	reference is a placebo
Statistical Methodology	Repeated measures analysis using mixed linear models

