4.2 Toxicities and Dosing Delays/Dose Modifications

Lanthanum carbonate may lower blood phosphate levels and can be associated with gastrointestinal side effects including nausea, vomiting, constipation and diarrhea.

Nicotinamide may lower blood phosphate levels and may be associated with other laboratory abnormalities including thrombocytopenia, abnormalities in liver function tests and CK. Gastrointestinal side effects, such as diarrhea and heartburn may also occur.

The following laboratory results are **expected study adverse events**:

- **Hypophosphatemia:** Plasma phosphate level <1.5 mg/dl
- **Thrombocytopenia:** Platelet count <100,000
- **Liver function test abnormalities:** AST, ALT, total bilirubin, alkaline phosphatase > 4 times the upper limit of the core lab (fill in precise numbers when the lab is named)
- **Elevated Creatine Kinase:** Creatine Kinase > 4 times upper limit of normal

The following symptoms are **expected study adverse events**:

- **Bruising**
- **Bleeding**
- **Severe diarrhea**
- **Severe nausea**
- **Flushing**
- **Hives**

Each patient will be assessed for the development of toxicity at each study visit (see section 5.4).

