5.0 STUDY PROCEDURES

There are 8 expected visits for the entire study. Study visits baseline 1 and follow-up 5 will take place at the NUCATS Clinical Research Center (CRU). The remaining visits will be completed at the Center for Translation Metabolism and Health (CTMH).

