11.4 Subject Compensation

Subjects will receive compensation per study consent form. Study compensates \$50.00, in the form of a check, for each of the 8 study visits. Total compensation, excluding reimbursement for travel expenses, is \$400.00. Subjects will be required to submit proof of travel expenses (i.e., receipts) to study staff in order to be reimbursed for travel expenses. Travel expenses will be paid out in the form of a check as well.

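### No contact is scheduled after F5 (Day 12), so new serious adverse events are not actively sought for most or all of the 30-day post-dose window

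*Combined protocol and SAP*

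**What the plan says.** **Reporting window.** Section 7.4.1 requires the Principal Investigator to be told, within 24 hours of staff learning of them, of serious events "occurring during the study or within 30 days of the last administration of the study drug". Section 7.3 says of the events to be assessed: "This includes all events that occur within 30 days of the last dose of protocol treatment". It adds later events if they are attributed to the study agents.

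**Contacts.** Section 5.0 states: "There are 8 expected visits for the entire study". Section 11.4 pays "for each of the 8 study visits". The eight are S1, B1, B2/F0 and F1 to F5, and the day row in 5.5 ends at Day 12. Section 4.2 ties toxicity checks to those visits: "Each patient will be assessed for the development of toxicity at each study visit (see section 5.4". The row in 5.5 for "Adverse events assessment (labs and GI questionnaire" ends at F5.

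**Length of participation.** The Study Summary gives the duration of administration as "2 weeks (length of time study participants are enrolled in study". Section 4.5 sets therapy at two weeks, and section 4.6 separately sets follow-up at two weeks.

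**Follow-up of known events.** Section 7.1 says: "All patients experiencing an adverse event, regardless of its relationship to study drug/device, will be monitored until" one of its listed end-points is reached, such as resolution. Section 7.6.1 adds a visit after a plasma phosphate below 1.5 mg/dl. Section 7.5 allows unblinding when clinical care depends on it.

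**The concern.** The protocol sets its own post-dose window of 30 days, yet its schedule stops at about the end of dosing. Staff who follow sections 5.4 and 5.5 exactly would not ask any completer about new events after F5. A serious event starting after that visit in someone with nothing open would reach the investigator through no planned step. An absence of late reports could then mean that nothing happened or that nobody was asked. What is at stake is how the post-dose safety record in healthy volunteers can be read. The efficacy endpoints are not involved.

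**Working it through.** **Inputs.** Post-dose window 30 days (7.3, 7.4.1). Course 14 days (4.1.2). Visit days -15, -5, -2, 0, 3, 6, 9, 12 (5.5). Randomization and dispensing at B2/F0 (5.4.1). 80 participants, 20 per group (10.1).

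**1. The schedule.** Eight visit labels set against eight day values put B2/F0 at Day -2 and F5 at Day 12. This matches the eight visits in 5.0 and 11.4. The 5.5 table is broken in the available text, and its randomization mark may belong to Day 0, so both starts are carried forward.

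**2. Completers.** Last dose = first dose + 13. The window runs from last dose + 1 to last dose + 30.
- Start Day -2: last dose Day 11, window Days 12 to 41. Days after F5: 41 - 12 = 29 of 30.
- Start Day 0: last dose Day 13, window Days 14 to 43. All 30 days fall after F5.

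F5 is thus one day after the last dose or one day before it.

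**3. Early stoppers who keep attending.** For a last dose on Day L, the days left after F5 are min(30, L + 18).
- L = -2: 16 days.
- L = 3: 21 days.
- L = 9: 27 days.

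**4. Section 4.6 read as follow-up after therapy.** 30 - 14 = 16 days remain. Against that reading, 5.5 uses its follow-up label for F1 to F5, and the Study Summary makes enrolment two weeks in all. No contact is listed for such a period in any case.

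**5. Provisions that might fill the gap.** Sections 7.1, 7.5 and 7.6.1 each act on an event or result already known. None looks for a new event in someone who was well at F5.

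**6. What asking could establish.** With no events among n people asked, the one-sided 95% upper limit is 1 - 0.05^(1/n).
- n = 20 (combination group): 13.9%.
- n = 60 (all on at least one active agent): 4.9%.
- With 80% reached (an assumption), n = 16: 17.1%; n = 48: 6.1%.

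If nobody is asked, there is no known denominator and no limit can be stated.

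**The case against.** The strongest reply is that nothing here is wrong. Section 7.4.1 starts a clock when staff learn of an event and promises no contact, and 7.3 is a rule for classifying and reporting. That stands: a reader might infer that the window and the schedule contradict each other, but the text does not support it.

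The stakes also look low. Exposure lasts two weeks. Section 1.2 describes nicotinamide as safe at high doses and cites six-year safety data and healthy-volunteer use for lanthanum carbonate. Phosphate, platelets, liver tests and CK are checked about every three days up to F5. A reader might infer from the remark in 10.2 about missing combination data that a late hazard is going unseen. That remark explains the sample-size assumptions, and no section names a delayed toxicity.

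A reader might also multiply the uncovered days by the number of participants to size the problem. That would mislead. One call at about day 30 leaves nearly all those days without contact; what it adds is a retrospective question. Early stoppers and people followed under 7.1 also have more contact than completers with nothing open. The limits of 13.9% and 4.9% are wide, and estimating a late-event rate is not a trial objective.

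Finally, the consent pages are not available. They may tell participants how to report events, and a contact described there cannot be excluded. What survives is narrow: the schedule in the protocol contains no step that asks about new events after F5.

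**Conclusion.** The point holds as a modest, low-priority gain in safety ascertainment and not as an error. For completers with no open event at F5, new serious events are not actively sought on 29 of 30 post-dose days (dosing from Day -2) or on all 30 (dosing from Day 0). On the less likely reading of 4.6 the figure is 16 days. This rests on a 14-day course taken in full, F5 on Day 12, and no contact described only in the missing consent pages.

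The day counts describe the schedule and not a risk: how many events might be missed, if any, cannot be computed from the documents. Endpoints, tests and power are unaffected.

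**What to change.** Add to 5.5 one scripted telephone contact by existing staff, in all four arms so that the blind is kept. Place it on or within about 7 days after the 30th day after the actual last dose. For completers that means from Day 41 (dosing from Day -2) or Day 43 (dosing from Day 0). Ask about new serious adverse events since F5 and about any event still open at F5. Change 5.0 to eight visits and one telephone contact, and align 4.6 and the enrolment line in the Study Summary. Dosing, dispensing and F5 stay as they are.

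**Cost.** About 80 short calls. At an assumed 5 to 15 minutes each, 80 x 5 = 400 minutes (6.7 hours) to 80 x 15 = 1,200 minutes (20 hours) in total. Section 11.4 pays per visit, so a call adds no payment as written.

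**Downsides.** Answers rest on recall, and some participants will not be reached. The call also cannot capture attributed events that occur after it, which 7.3 keeps in scope. The amendment needs IRB approval (11.7) and possibly one added sentence in the consent form.

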7.4.2 Routine Reporting

- All other adverse events- such as those that are expected, or are unlikely or definitely not related to the study participation- are to be reported annually as part of regular data submission.

7.5 Unblinding Procedures

When a participant stops his or her blinded nicotinamide and lanthanum carbonate and appropriate clinical management of the participant is dependent on knowledge of whether the participant had been taking active nicotinamide or active lanthanum carbonate, the research pharmacist will unblind the investigator to the necessary arm.

7.6 Stopping Rules**7.6.1 Hypophosphatemia**

If a study participant has a plasma phosphate level lower than 1.5 mg/dl, an extra visit will be held immediately so the test can be repeated. If the second lab test confirms a plasma phosphate level under 1.5 mg/dl, then both study medications should be stopped.

7.6.1 Other side effects

If a study participant develops any of the following expected study adverse events, study interventions will be stopped:

- Thrombocytopenia: Platelet count <100,000
- Liver function test abnormalities: AST, ALT, total bilirubin, alkaline phosphatase > 4 times the upper limit of the core lab (fill in precise numbers when the lab is named)
- Elevated Creatine Kinase: Creatine Kinase > 4 times upper limit of normal
- Severe bleeding
- Severe diarrhea
- Severe nausea
- Severe Flushing
- Hives

8.0 DRUG/DEVICE INFORMATION**8.1 Lanthanum Carbonate**

- Fosrenol
- Classification – phosphate binder
- Mode of action: binds intestinal phosphate
- Storage and stability: stable at room temperature; protect from moisture
- Protocol dose: 1000 mg by mouth three times daily with meals
- Preparation: chewable tablet
- Route of administration for this study: by mouth

- Incompatibilities: N/A
- Availability: provided free of charge by manufacturer
- Side effects: hypophosphatemia, nausea, vomiting, diarrhea, abdominal discomfort
- Nursing implications: none

8.2 Nicotinamide

- Niacinamide
- Classification – vitamin
- Mode of action: blocks phosphate absorption through gut sodium phosphate channel
- Storage and stability: stable at room temperature; protect from moisture
- Protocol dose: 750 mg by mouth twice daily
- Preparation: tablet, oral
- Route of administration for this study: by mouth
- Incompatibilities: N/A
- Availability: provided free of charge by manufacturer
- Side effects: hypophosphatemia, nausea, vomiting, diarrhea, abdominal discomfort
- Nursing implications: none

